7. GENERAL CONSIDERATIONS

7.1. REFERENCE START DATE AND STUDY DAY -

Study Day will be calculated from the reference start date and will be used to show start/stop day of assessments and events.

Reference start date is defined as the day of the first dose of any study medication, (Day 1 is the day of the first dose of any study medication).

If the date of an event is on after the reference date, the following will be calculated:

- study day = date of event – reference date + 1
- cycle day = (date of an event – date of earliest administration of Nivolumab and/or Debio 1143 in Cycle n) + 1, where date of an event < date of earliest administration of Nivolumab and/or Debio 1143 in Cycle n

In listings, an assessment date will be supported by the cycle number/day which takes the format CxDy, where Cx is the cycle number as recorded in the study exposure (nivolumab) eCRF and Dy is the cycle day.

If the date of an event is prior to the reference date, then:

- Study Day = date of event – reference date

Document: T:\sas\Debiopharm\Debio_1143\CZA60507\Biostatistics\Documentation\SAP\SAP Text\V5

Author: XXXXXXXXXX Version Number: 5.0
Version Date: 19APR2022

Template No.: CS_TP_BS016 Revision 5
Effective Date: 01Apr2018

Reference: CS_WI_BS005

In the situation where the event date is partial or missing, study day, and any corresponding durations will not be calculated.

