**Table 1-1 Schedule of assessments**

CYCLE DAY*	Screening -28 to -1	CYCLE															EOT	Follow-up#	EOS		
		Baseline		1					2		3				4-13					>13 	
		1	3 	8	15	17 	22	1	15	1	3 	15	17 	1	15	1				15	
INFORMED CONSENT	X	-	-	-	-	-	-	-	-	-	-	-	-	-	-	-	-	-	-	-	
MEDICAL AND MEDICATION HISTORY 	X	X	-	-	-	-	-	-	-	-	-	-	-	-	-	-	-	-	-	-	
INCLUSION/EXCLUSION CRITERIA	X	X	-	-	-	-	-	-	-	-	-	-	-	-	-	-	-	-	-	-	
PHYSICAL EXAMINATION	X 	X	-	-	X	-	-	X	X	X	-	X	-	X	-	X	-	X	-	-	
ECOG, VITAL SIGNS	X	X	-	X	X	-	X	X	X	X	-	X	-	X	X	X	-	X	-	-	
CONCOMITANT MEDICATIONS	X	X	X	X	X	X	X	X	X	X	-	X	-	X	X	X	-	X	X	-	
DIGITAL, TRIPPLICATED 12-LEAD ECG 	X	X	-	X	X	-	X	-	-	X	-	-	-	-	-	-	-	-	-	-	
SAFETY LABORATORY SAMPLING 	X 2a,b,c,f	X 2c,e	X 2d	X 2c	X 2c,e	X 2d	X 2c	X 2c,e,f	X 2c	X 2c,e,f	-	X 2c	-	X 2c,e,f	-	X 2c,e,f	-	X 2c,e	-	-	
PREGNANCY TEST 	X	X	-	-	-	-	-	X	-	X	-	-	-	X	-	X	-	X	X	-	
CT SCAN OR MRI 	X	-	-	-	-	-	-	-	X	-	-	-	-	-	X	X	-	X	X	-	
TUMOR BIOPSY 	X	-	-	-	-	-	-	-	-	Optional	-	-	-	-	-	-	-	-	-	-	
PK SAMPLING 	-	X	X 6a	X	X	X 6a	X	-	-	X	X 6a	X	X 6a	X 6b	-	X 6b	-	X 6b	-	-	
PDY AND PREDICTIVE BM SAMPLING 	-	X	-	X	X	-	X	-	-	X	-	-	-	X 7a	-	-	-	-	-	-	
DEBIO 1143 DISPENSING/ACCOUNTABILITY 	-	X	-	-	X	-	-	X	X	X	X	X	-	X	X	X	-	-	-	-	
NIVOLUMAB DISPENSING/ACCOUNTABILITY 	-	X	-	-	X	-	-	X	X	X 9a	-	+/-	-	X 9a	+/-	X 9a	+/-	-	-	-	
ADVERSE EVENTS	X	X	X	X	X	X	X	X	X	X	X	X	X	X	X	X	-	X	X 	-	

**Cycle:** Each cycle is defined as 28 days

**EOT:** A visit should be performed 30 days (± 5days) after last Debio 1143 dose, unless start of new cancer treatment or end-of-life care before, in which case EOT visit should be ideally scheduled immediately before these events.

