16.1. DERIVATIONS

- Treatment compliance (%) = $(\text{actual cumulative dose} / \text{planned cumulative dose}) * 100$

Planned dose by cycle:

- Debio 1143 (mg): $20 * 200 = 4000$
- Nivolumab (mg): 480

Planned cumulative dose:

Document: T:\sas\Debiopharm\Debio_1143\CZA60507\Biostatistics\Documentation\SAP\SAP Text\V5

Author: XXXXXXXXXX Version Number: 5.0
 Version Date: 19APR2022

Template No.: CS_TP_BS016 Revision 5
 Effective Date: 01Apr2018

Reference: CS_WI_BS005

Copyright © 2009, 2010, 2012, 2016, 2018 IQVIA. All rights reserved. The contents of this document are confidential and proprietary to IQVIA Holdings Inc. and its subsidiaries. Unauthorized use, disclosure or reproduction is strictly prohibited.

- Debio 1143 (mg): Number of cycles started x Planned dose by cycle
- Nivolumab (mg): Number of cycles started x Planned dose by cycle

When Debio 1143 is ongoing, cycle starts if at least one dose of Debio 1143 > 0 is received on Day 1. Cycle period is defined from Day 1 of current cycle to day before Day 1 of the next cycle.

If Debio 1143 stopped but Nivolumab is ongoing, cycle period is defined as 28 days, continuing from the date of last Debio 1143 administration >0. (ie. For example, if last Debio 1143 administration is on 1APR21 corresponding to C4D17, next Nivolumab administration received on 14APR21 would correspond to C5D2).

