18.1. ADVERSE EVENTS

AEs as recorded in the Adverse Events eCRF will be coded using the most up-to-date version of the MedDRA central coding dictionary at the time of analysis.

TEAEs are defined as AEs that started or worsened in severity on or after the first dose of any study medication and prior to the last date of nivolumab + 5 months or the earliest date of new anticancer therapy – 1 day, whichever occurs first.

See section 8.2.1 for handling of partial dates for AEs. In the case where it is not possible to define an AE as treatment emergent or not, the AE will be classified by the worst case; i.e. treatment emergent.

AEs will be graded according to NCI-CTCAE version 5.0

An overall summary of number of subjects within each of the categories described in the sub-sections below, will be provided as specified in the templates.

Listings will include TEAEs, Non-TEAEs and TEAEs leading to discontinuation of Debio 1143.

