18.1.3. TEAEs WITH GRADE 3 OR HIGHER

TEAEs with grade 3 or higher are those events recorded on the eCRF where “NCI CTCAE Grade V5.0 Criteria” is answered as “Grade 3”, “Grade 4” or “Grade 5”.

TEAEs with grade 3 or higher will be presented by the following:

- SOC/PT and relatedness to study drugs (related to Debio 1143, related to nivolumab and related to both)
- PT and relatedness to study drugs
- SOC/PT and by cycle

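### The cycle-day rule in SAP 7.1 cannot work as written, and the SAP does not say which cycle a TEAE after the last cycle belongs to

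*SAP*

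**What the plan says.** - **Cycle day.** SAP 7.1 defines cycle day as the event date minus the earliest administration of either drug in Cycle n, plus 1, "where date of an event < date of earliest administration of Nivolumab and/or Debio 1143 in Cycle n". In listings the label is CxDy, "where Cx is the cycle number as recorded in the study exposure (nivolumab) eCRF and Dy is the cycle day".
- **Cycle period.** SAP 16.1, which derives compliance, covers two situations. While Debio 1143 is ongoing, "Cycle period is defined from Day 1 of current cycle to day before Day 1 of the next cycle". Otherwise, "If Debio 1143 stopped but Nivolumab is ongoing, cycle period is defined as 28 days".
- **Nominal length.** The schedule of assessments in the protocol (Table 1-1) states: "Each cycle is defined as 28 days".
- **TEAE window.** SAP 18.1 counts events from the first dose and "prior to the last date of nivolumab + 5 months", or up to the day before new anticancer therapy if that is earlier.
- **By-cycle output.** SAP 18.1.3 tabulates grade 3 or higher TEAEs by "SOC/PT and by cycle". By-cycle tables are also planned for all TEAEs (18.1.1), Debio 1143-related TEAEs (18.1.4), dose modification and discontinuation (18.1.7 to 18.1.12), serious events (18.1.13), common events (18.1.15), special-interest events (18.1.16) and laboratory grades (18.3). The SAP text gives none of them a post-treatment category and does not say which rule places a TEAE in a cycle.

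**The concern.** By-cycle tables are there to show when toxicity occurs. That needs a rule placing each event in one cycle, and a boundary between the last cycle and follow-up. The printed rule in 7.1 does the first incorrectly, and no section does the second for these tables.

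The boundary matters because the TEAE window is long compared with a cycle. Take a patient who stops in Cycle 1 and has an immune-related event months later. If the last cycle is left open, that event is reported under Cycle 1. Early-cycle incidence would then be overstated, most of all where patients leave early, and the tables would misstate the timing of late events.

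**Working it through.** **Inputs.** Cycle length is 28 days (protocol Table 1-1). Nivolumab is given on Days 1 and 15, or on Day 1 only after the permitted switch (protocol 5.3). The TEAE window is that of SAP 18.1. Five months is taken as 150 to 153 days (assumption).

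**1. The plan's own example.** SAP 16.1 says that if 1APR21 is C4D17, the "next Nivolumab administration received on 14APR21 would correspond to C5D2".
- C4D1 = 1APR21 − 16 days = 16MAR21.
- 14APR21 − 16MAR21 + 1 = 30, and 30 − 28 = 2, which gives C5D2. The example reproduces with 28-day cycles.

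**2. The 7.1 rule as printed.** Let E be the event date and S_n the first dose of Cycle n. Cycle day = E − S_n + 1, subject to E < S_n. Since E − S_n is at most −1, cycle day is at most 0. With four 28-day cycles starting on study days 1, 29, 57 and 85:

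| Event (study day) | As printed | With S_n ≤ E < S_(n+1), last cycle left open |
|---|---|---|
| 1 | Cycles 2, 3, 4: days −27, −55, −83 | C1D1 |
| 36 | Cycle 3: 36 − 57 + 1 = −20; Cycle 4: 36 − 85 + 1 = −48 | 36 − 29 + 1 = 8, C2D8 |
| 105 | no cycle qualifies | 105 − 85 + 1 = 21, C4D21 |
| 251 (152 days after a Day 15 infusion in Cycle 4: 85 + 14 + 152) | no cycle qualifies | 251 − 85 + 1 = 167, C4D167 |

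Taking the cycle number from the nivolumab eCRF does not rescue the rule. For the day 36 event the eCRF cycle is 2, but 36 < 29 is false, so no cycle day is returned.

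**3. Length of an open last cycle.** If the last nivolumab dose is on cycle day d and the window is m days, the last cycle reaches day d + m, counting the closing date. A strict reading of the SAP's wording takes off one day.
- d = 1: 1 + 150 = 151 to 1 + 153 = 154.
- d = 15: 15 + 150 = 165 to 15 + 153 = 168.
- Days past Day 28: 151 − 28 = 123 to 168 − 28 = 140.
- Ratio to 28 days: 151/28 = 5.4 to 168/28 = 6.0.

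**4. Share of events past Day 28, at a constant event rate (assumption).**
- Full window: 1 − 28/151 = 81.5% to 1 − 28/168 = 83.3%.
- New therapy 42 days after a Day 15 infusion (assumption): it starts on day 15 + 42 = 57, so the window closes on day 56, and 1 − 28/56 = 50%.

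**The case against.** A reader might infer that the SAP counts late TEAEs in the last cycle. No section says so. Read literally, 7.1 gives those events no cycle, and 16.1 exists to count cycles for planned dose. The table shells are separate documents not available here and may contain a follow-up column. This stands, so the allocation is a likely default and no more.

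The last cycle is not open in every case. SAP 16.1 has a 28-day branch, the protocol's nominal cycle is 28 days, and protocol 11.6.4.2 defines an on-treatment window of last nivolumab plus 14 or 28 days. This stands in part. The 28-day branch applies only while nivolumab continues after Debio 1143 has stopped. Protocol 5.4 has patients who stop Debio 1143 definitively also stop nivolumab, so the open-ended branch is the usual one. Neither 16.1 branch covers the period after both drugs have stopped. The SAP applies neither the nominal length nor the protocol window to its by-cycle TEAE tables.

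The figures are upper limits. The window closes early at new anticancer therapy, protocol 8.2.2.1 also stops AE recording when end-of-life care starts, and death ends it. After the end-of-treatment visit, AEs are reviewed at no more than two follow-up visits. Nothing in the documents supports a constant event rate out to month five. TEAEs that lead to dose reduction, omission or a slower infusion concern ongoing dosing and can add little to the tail. This stands.

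It is also tempting to say that late toxicity is hidden or that the dose decision is at risk. Overall TEAE tables, study day and the TEAE listings are unaffected. DLTs come from an eCRF flag confirmed at the dose decision (SAP 18.1.2). No efficacy endpoint, futility rule or analysis set uses cycle day.

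**Conclusion.** Two things follow directly from the text. The 7.1 condition is wrong as printed: it can return only zero or negative cycle days, and none for the last cycle. Whether the sign is reversed or n+1 was dropped cannot be settled from the documents, and both lead to the same correction. Second, the SAP text does not define how TEAEs after the last cycle are assigned in its by-cycle tables.

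That such events land in the last cycle started is an inference. It rests on correcting 7.1, on using the main 16.1 cycle period, and on the shells adding no other rule. Under those assumptions the last cycle reaches at most about day 151 to 168, or 5.4 to 6.0 times its nominal length. The 82% to 83% share past Day 28 needs a constant rate and the full window; it falls to 50% if new therapy starts six weeks after a Day 15 infusion. None of these is a prediction for a typical patient.

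The effect is confined to descriptive by-cycle safety tables. Overall TEAE incidence, DLTs and efficacy results do not change.

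**What to change.** 1. In SAP 7.1, replace the condition with: first administration in Cycle n ≤ event date < first administration in Cycle n+1.
2. Close the last cycle at a prespecified analysis end consistent with the protocol. One option is the later of Day 28 and the protocol 11.6.4.2 window of last nivolumab plus 14 or 28 days. At nominal dosing that gives Day 29 (15 + 14, or 1 + 28), and it extends if the last infusion is late. A fixed Day 28 alone would fit poorly with protocol 5.1.1, which lets Cycle 1 run longer than four weeks when dosing is delayed.
3. Report later TEAEs in a separate post-treatment column, with its own stated denominator.
4. State that this one rule governs the by-cycle tables in 18.1 and 18.3, and check that the table shells agree.

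The cost is SAP wording and one extra table column. No new data are needed.

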7.2. BASELINE

Unless otherwise specified, baseline is defined as the last non-missing measurement taken prior to reference start date (including unscheduled assessments).

If an assessment is planned to be performed prior to the first dose of study treatment in the protocol and the assessment is performed on the same day as the first administration of study drug, it will be assumed that it was performed prior to study treatment administration (if time is not available).

7.3. DERIVED TIMEPOINTS

There will be no derived timepoints for by-visit analyses. The data will be presented by visit as recorded in the eCRF.

7.4. UNSCHEDULED VISITS

In general, for by-visit summaries, data recorded at the nominal visit will be presented (including early termination visit like “end of treatment” or “end of study”). Unscheduled measurements will not be included in by-visit summaries but will contribute to the best/ worst case value where required (e.g. shift table). Listings will include both scheduled and unscheduled data.

All tumour assessment and/or CA-125 data from both scheduled and unscheduled visits will be included in the analyses described in section 17 of this SAP.

7.5. WINDOWING CONVENTIONS

Regarding PK data, concentrations with actual sampling time outside the windows of tolerance specified in Table 8-5 of protocol will be only excluded from the PK analyses in case of pre-dose concentrations.

7.6. STATISTICAL TESTS

The default significant level will be 5%; confidence intervals (CIs) will be 95% and all tests/CIs will be two-sided,

Document: T:\sas\Debiopharm\Debio_1143\CZA60507\Biostatistics\Documentation\SAP\SAP Text\V5

Author: XXXXXXXXXX Version Number: 5.0
Version Date: 19APR2022

Template No.: CS_TP_BS016 Revision 5
Effective Date: 01Apr2018

Reference: CS_WI_BS005

unless otherwise specified in the description of the analyses.

Ordinal and continuous data will be presented in the form of descriptive statistics, as the number of observations, mean, standard deviation, minimum, 25th percentile (Q1), median, 75th percentile (Q3), maximum and two-sided 95% CI.

Categorical data will be presented using contingency tables with absolute and relative frequencies. Missing data will be considered as a category and included in the calculation of percentages, unless otherwise stated.

For time-to-event endpoints, Kaplan Meier (K-M) estimates will be provided and include number and percentage of events/censored, minimum, Q1, median, Q3 and maximum survival time and associated two-sided 95% CI obtained using the Brookmeyer-Crowley method. The progression-free survival rate and two-sided 95% CI at pre-specified time points will also be provided. In this case, Greenwood's formula will be used for the 95% CI.

For PK parameters and concentrations, summary statistics in the tabulation will include number of non-missing value, number below the lower limit of quantification (LLOQ), mean, standard deviation, minimum, Q1, median, Q3, two-sided 95% CI of the arithmetic mean, coefficient of variation (CV%), maximum, geometric mean, two-sided 90% CI of the geometric mean, geometric standard deviation [calculated as: $\text{geo standard deviation} = \exp(\text{SD}_{\log})$], and geometric CV% [calculated as: $\text{geo CV\%} = \text{SQRT}(\exp(\text{SD}_{\log}^2) - 1) * 100\%$]; where SD_{\log} is the standard deviation of the log-transformed values.

The minimum and maximum will be reported to the same number of decimal places as the raw data recorded in the database. The mean, median, Q1 and Q3 will be reported to one more decimal place than the raw data recorded in the database. The standard deviation will be reported to two more decimal places than the raw data recorded in the database. If raw data recorded have more than 1 decimal places, minimum and maximum will be reported to 1 decimal place, mean, median, Q1 and Q3 will be reported to 2 decimal place and standard deviation will be reported to 3 decimal place. Percentages will be reported with one decimal place. The CV% is reported as a percentage with 1 decimal places.

7.7. SOFTWARE VERSION

All analyses will be conducted using SAS version 9.4 or higher. For the PK analyses using non-compartmental method, WinNonlin version 8.1 or higher (Certara, L.P., Princeton, New Jersey) will be used.

Document: T:\sas\Debiopharm\Debio_1143\CZA60507\Biostatistics\Documentation\SAP\SAP Text\V5

Author: [REDACTED] Version Number: 5.0
Version Date: 19APR2022

Template No.: CS_TP_BS016 Revision 5
Effective Date: 01Apr2018

Reference: CS_WI_BS005

Copyright © 2009, 2010, 2012, 2016, 2018 IQVIA. All rights reserved. The contents of this document are confidential and proprietary to IQVIA Holdings Inc. and its subsidiaries. Unauthorized use, disclosure or reproduction is strictly prohibited.

8. STATISTICAL CONSIDERATIONS

8.1. MULTICENTER STUDIES

Center pooling will not be carried out for use in analyses for this study.

Statistical tests and models will not be adjusted for the sites, and no analysis exploring the homogeneity of the results from one site to the other will be performed.

8.2. MISSING DATA

8.2.1. ADVERSE EVENTS

When the day of onset of an AE is missing:

- If month and year of onset of an AE is the same as the month and year of date of first administration of the study drug and the end date is not before the date of first dose, then the missing day is imputed by the day of date of first administration of the study drug
- Otherwise, the missing day is imputed by 1st of the month.

When the day and month of onset of an AE are missing

- If year of onset of an AE is the same as the year of date of first administration of the study drug and the end date is not before the date of first dose, then the missing day and month are imputed by the day and month of date of first administration of the study drug
- Otherwise, the missing day and month are imputed as January 1st

If onset date is completely missing:

- If AE end date is on/after the date of first administration of the study drug, then onset date is set to date of first administration of the study drug
- If AE end day or month are missing, then AE end day will be imputed as last day of the month and AE end month will be imputed as December.
 - o If imputed end date is on or after the date of first administration of the study drug, then onset date is set to date of first administration of the study drug and AE is considered as treatment-emergent
 - o If AE end date is prior to the date of first administration of the study drug, then onset date is not imputed, and AE is not considered as treatment-emergent

Document: T:\sas\Debiopharm\Debio_1143\CZA60507\Biostatistics\Documentation\SAP\SAP Text\V5

Author: XXXXXXXXXX Version Number: 5.0
Version Date: 19APR2022

Template No.: CS_TP_BS016 Revision 5
Effective Date: 01Apr2018

Reference: CS_WI_BS005

8.2.2. CONCOMITANT MEDICATIONS AND PROCEDURES/NON-PHARMACOLOGICAL TREATMENTS

- End date: Missing day will be imputed as the last day of the month, and missing month will be imputed as December.
- Start date: Missing day will be imputed as the 15th, and missing month will be imputed as June. If the start date is completely missing, then:
 - o If the end date is prior to the date of first administration of the study drug, then the medication is considered as a pre-medictaion
 - o If the end date is prior to the date of last administration of the study drug, then the medication is considered as a co-medication
 - o If the end date is completely missing or after the date of last administration of the study drug, then the medication is considered as pre, co and post.

If after imputation, start date > end date, then start date will be replaced by end date.

Subsequent anti-cancer therapies partial dates will be imputed as follow:

- End date: no imputation
- Start date: Missing day will be imputed as the 15th, and missing month will be imputed as June. If after imputation, start date <= date of last study treatment administration, then set start date to date of last study treatment administration + 1

If after that, start date > end date, then start date will be replaced by end date.

8.2.3. EFFICACY

Missing efficacy data will be handled as described in section 17 of this analysis plan.

8.3. MULTIPLE COMPARISONS/ MULTIPLICITY

Given the exploratory nature of this study (i.e., no formal sample size computation was performed), no methods for handling multiplicity will be implemented for this study.

8.4. EXAMINATION OF SUBGROUPS

No subgroup analyses will be performed for this study.

Document: T:\sas\Debiopharm\Debio_1143\CZA60507\Biostatistics\Documentation\SAP\SAP Text\V5

Author: XXXXXXXXXX Version Number: 5.0
Version Date: 19APR2022

Template No.: CS_TP_BS016 Revision 5
Effective Date: 01Apr2018

Reference: CS_WI_BS005

Copyright © 2009, 2010, 2012, 2016, 2018 IQVIA. All rights reserved. The contents of this document are confidential and proprietary to IQVIA Holdings Inc. and its subsidiaries. Unauthorized use, disclosure or reproduction is strictly prohibited.

9. OUTPUT PRESENTATIONS

Appendix 1 shows conventions for presentation of data in outputs.

The templates provided with this SAP describe the presentations for this study and therefore the format and content of the summary tables, figures, and listings to be provided by IQVIA Biostatistics.

All endpoints such as demographics, baseline characteristics, safety, PK, PDy, etc. will be presented overall and by dose level for Part A and cohort for Part B.

All outputs will be presented for both Part A and Part B separately.

For Part B, the efficacy outputs will be reported by cohort.

10. DISPOSITION AND WITHDRAWALS

10.1. SUBJECT DISPOSITION

A summary on the SCR analysis set will include the number and the percentage of:

- Subjects screened (only frequency will be presented),
- Subjects screen failed with reasons
- Subjects enrolled (“Did the subject continue beyond screening” = yes as per the “Eligibility Criteria” eCRF page)
- Number of patients not treated with Debio 1143 and/or nivolumab, if applicable
- Treated subjects including
- End of treatment status (ongoing, discontinued) with reason for treatment discontinuation
- End of study status (completed, ongoing, discontinued) with reason for study discontinuation.
- Subjects in each of the study analysis sets

Subjects excluded from each analysis set out of the ITT/Safety analysis set will be tabulated by reason for exclusion.

All subject disposition data will be presented in data-listings. Screening failure and reasons will be listed separately.

Reason of exclusion from each analysis set will be listed.

Document: T:\sas\Debiopharm\Debio_1143\CZA60507\Biostatistics\Documentation\SAP\SAP Text\V5

Author: XXXXXXXXXX Version Number: 5.0
Version Date: 19APR2022

Template No.: CS_TP_BS016 Revision 5
Effective Date: 01Apr2018

Reference: CS_WI_BS005

Copyright © 2009, 2010, 2012, 2016, 2018 IQVIA. All rights reserved. The contents of this document are confidential and proprietary to IQVIA Holdings Inc. and its subsidiaries. Unauthorized use, disclosure or reproduction is strictly prohibited.

